3.2 Per Protocol Analysis Set

PPS will include all patients in the FAS who have no major protocol deviations. Examples of major deviations are:

- Violations of inclusion/exclusion criteria
- The use of prohibited or discourage medication
- Gross violation of visit schedules

Patients will contribute to the analysis ‘as treated’.

3.3 Safety Analysis Set

The SAF consists of all treated patients that received any amount of study medication (imlifidase or PE). Patients will contribute to the analysis ‘as treated’.

3.4 Pharmacokinetic Analysis Set

PKS will include patients receiving any amount of imlifidase. It will also be further defined by the PK analyst taking admission criteria, protocol deviations and other non-compliance into consideration.

4 Statistical analyses and presentation of data

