In addition, the reduction of total serum IgG levels will be analyzed as a binary endpoint. The binary endpoint is defined as a success, if the minimum IgG value at any time point during the 5 days following the start of treatment is less than 5% of baseline for the patient. The proportion of patients, which satisfy the success criterium, will be presented in a summary table by treatment. The difference in proportion between the two treatments will be presented with a 95% CI in a summary table. The 95% CI for the difference between the two treatments will be based on exact Confidence Limits. In addition, the proportion of patients which satisfy the success criterium will be presented by treatment and time point.

The composition of IgG-fragments will be analyzed centrally using SDS-PAGE. Each sample will be assigned a score depending on the observed composition of fragments as follows:

- 0=no intact IgG, scIgG or F(ab')₂
- 1=only F(ab')₂
- 2=mix of scIgG and F(ab')₂
- 3=only scIgG
- 4=mix of intact IgG and scIgG
- 5=only intact IgG

SDS-PAGE scores will be summarized by time point.

Presence of intact IgG on SDS-PAGE until start of IVIg treatment

The endpoint is a success for a patient if no detectable intact IgG is found by the SDS-PAGE assay for at least one time point between the start of study medication (imlifidase) treatment and start of administration of IVIg. No detectable intact IgG is defined as SDS-PAGE scores 0, 1, 2 or 3. The

proportion of patients, who reached the success criterium, will be summarized in a table using the PKS set.

Number of patients with resolution of AMR at day 180

The number of patients with resolution of AMR at day 180 will be handled as a binary variable. Resolution is defined as “Active AMR” or “Chronic active AMR” not being selected from the biopsy protocol.

The endpoint is a success if the patients have resolution of AMR at day 180. The proportion of patients, which satisfy the success criterium, will be tabulated by treatment. A list will be created by patient. The FAS set will be applied.

Patient survival at day 180

The patient survival on day 180 will be handled as a binary variable.

The endpoint is a success if the patients have survived on day 180. The proportion of patients, which satisfy the success criterium, will be summarized and listed by patient. The FAS set will be applied.

Pharmacokinetic

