4.7 Safety

Safety parameters will be evaluated for the safety analysis data set.

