4.7.2 Other safety endpoints

The clinical safety laboratory tests, vital signs, and ECG parameters will be summarised for both absolute values and changes from baseline by treatment and time point. The SAF set will be applied. The parameters will also be listed by patient. Values outside the reference ranges will be flagged in listings.

A list for physical examination will be created.

The results for the Polymerase Chain Reaction (PCR) tests for SARS-CoV-2 and pregnancy tests will be listed by patient.

Anti-implifidase antibody data (ADA) is numerical and will be summarized by time point in a summary table, where PKs is used. Anti-implifidase antibody data will also be presented graphically as boxplots and listed by patient.

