14.1.7	Table	Exposure (FAS)
EFFICACY DATA		
14.2.1	Table	Difference in maximum DSA reduction and 95% CI (FAS)
14.2.2	Table	Difference in maximum DSA reduction and 95% CI (PPS)
14.2.3	Table	DSA reduction - by time point (FAS)
14.2.4	Table	DSA reduction - by time point (PPS)
14.2.5	Table	MFI levels for DSA c1q - by time point (FAS)
14.2.6	Table	Proportion of patients with absence of graft loss at day 180 (FAS)
14.2.7	Table	Proportion of patients having no signs of transplant glomerulopathy at day 180 (FAS)
14.2.8	Table	Kidney biopsy (Banff) - Scores - by time point (FAS)
14.2.9	Table	Kidney biopsy (Banff) - Change from baseline (scores) - by time point (FAS)
14.2.10	Table	Kidney biopsy (Banff) - Interpretations - by time point (FAS)
14.2.11	Table	Kidney biopsy (Banff) - Shift table - by time point (FAS)
14.2.12	Table	Kidney biopsy () - Scores - by time point (FAS)
14.2.13	Table	Kidney biopsy () - Change from baseline - by time point (FAS)
14.2.14	Table	Number of sessions of PE and IA for 180 days (FAS)
14.2.15	Table	Total IgG - by time point (FAS)
14.2.16	Table	Proportion of patients having reduction in total IgG - by time point (FAS)
14.2.17	Table	Composition of IgG-fragments (SDS-PAGE) - by time point (FAS)
14.2.18	Table	Proportion of patients having no detectable intact IgG (PKS)
14.2.19	Table	Proportion of patients with resolution of AMR at day 180 (FAS)
14.2.20	Table	Patient survival at day 180 (FAS)
14.2.21	Table	Summary of imlifidase (PK) concentrations - by time point (PKS)
14.2.22	Table	Summary of imlifidase PK parameters (PKS)
DISPLAYS OF ADVERSE EVENTS		
14.3.1	Table	Overview of treatment-emergent AEs (SAF)
14.3.2	Table	Summary of treatment-emergent AEs - by SOC and PT (SAF)
14.3.3	Table	Summary of treatment-emergent AEs - by causality (SAF)

14.3.4	Table	Summary of treatment-emergent AEs - by intensity (SAF)
14.3.5	Table	Summary of related treatment-emergent AEs - by intensity (SAF)
14.3.6	Table	Summary of SAEs (SAF)
14.3.7	Table	Summary of SAEs - by causality (SAF)
14.3.8	Table	Summary of treatment-emergent SAEs (SAF)
14.3.9	Table	Summary of treatment-emergent SAEs - by causality (SAF)
14.3.10	Table	Summary of treatment-emergent SAEs leading to death (SAF)
14.3.11	Table	Summary of treatment-emergent AEs leading to withdrawal (SAF)
DISPLAYS OF SAFETY DATA		
14.4.1	Table	Summary of clinical chemistry variables - by time point (SAF)
14.4.2	Table	Summary of haematology variables - by time point (SAF)

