14.4.3	Table	Summary of coagulation variables - by time point (SAF)
14.4.4	Table	Summary of vital signs - by time point (SAF)
14.4.5	Table	Summary of ECG - by time point (SAF)
14.4.6	Table	Summary of anti-IdeS IgG (ADA) - by time point (PKS)
EFFICACY FIGURES		
15.1.1	Figure	DSA reduction vs time (FAS)
15.1.2-15.1.31	Figure	Individual plots DSA vs time (FAS)
15.1.32	Figure	Mean plot DSA level - by time point (FAS)
15.1.33	Figure	Individual IgG cleavage (PD) 0-180 days - by patient profiles (FAS)
15.1.34	Figure	Individual IgG cleavage (PD) 0-96 hours - by patient profiles (FAS)
15.1.35	Figure	Mean IgG cleavage (PD) - 0-180 days (FAS)
15.1.36	Figure	Mean IgG cleavage (PD) profile - 0-96 hours (FAS)
15.1.37	Figure	Mean log scale imlifidase concentration profiles (0-14 days) (PKS)
15.1.38	Figure	Mean log scale imlifidase concentration profiles (0-96 hours) (PKS)
15.1.39	Figure	Individual log scale PK concentration (0-14 days) - by patient profiles (PKS)
15.1.40	Figure	Individual log scale PK concentration (0-96 hours) - by patient profiles (PKS)
15.1.41	Figure	Anti-imlifidase IgG (ADA) - box plot (PKS)
PATIENT DATA LISTINGS		
BASELINE AND DEMOGRAPHIC DATA		
16.1.1.1	Listing	Patient disposition – by patient
16.1.1.2	Listing	Patients withdrawn from study – by patient
16.1.1.3	Listing	Protocol deviations - by patient (FAS)
16.1.1.4	Listing	Demography – by patient (FAS)

16.1.1.5	Listing	Medical and surgical history – by patient (FAS)
16.1.1.6	Listing	Concomitant medication – by patient (FAS)
16.1.1.7	Listing	Previous medication – by patient (FAS)
16.1.1.8	Listing	Previous kidney transplant history and donor type – by patient (FAS)
16.1.1.9	Listing	Compliance and exposure to study drug – by patient (FAS)
16.1.1.10	Listing	Compliance and exposure to IVIg – by patient (FAS)
16.1.1.11	Listing	Compliance and exposure to Rituximab – by patient (FAS)
INDIVIDUAL EFFICACY RESPONSE DATA		
16.2.1.1	Listing	DSA reduction - by patient and time point (FAS)
16.2.1.2	Listing	MFI levels for DSA c1q - by patient and time point (FAS)
16.2.1.3	Listing	All DSA - by patient and time point (FAS)
16.2.1.4	Listing	SAB-HLA MFI values - by patient and time point (FAS)
16.2.1.5	Listing	Patients with graft loss at day 180 - by patient (FAS)
16.2.1.6	Listing	Transplant glomerulopathy at day 180 - by patient (FAS)
16.2.1.7	Listing	Kidney Biopsy score and diagnose (Banff) - by patient and time point (FAS)
16.2.1.8	Listing	Kidney Biopsy score [REDACTED] - by patient and time point (FAS)

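### Anti-imlifidase antibodies and the SDS-PAGE intact-IgG success proportion are analysed in a PK set that the PK analyst may narrow, when only an imlifidase-only population is needed

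*SAP*

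**What the plan says.** SAP 3.4 defines the PKS in two steps. The entry rule is wide: "PKS will include patients receiving any amount of imlifidase". The second step leaves the final membership open: "It will also be further defined by the PK analyst taking admission criteria, protocol deviations and other non-compliance into consideration". Three grounds are named, but nothing says what kind or degree of deviation leads to removal. Protocol 12.1.4 is equally open.

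The SAP uses the set for concentrations and PK parameters, and also for two other results:

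- **ADA.** SAP 4.7.2, under other safety endpoints: "Anti-implifidase antibody data (ADA) is numerical and will be summarized by time point in a summary table, where PKs is used". In SAP section 8 the ADA table (14.4.6), the box plot (15.1.41) and the IgG and IgE listings (16.4.1.13, 16.4.1.14) all carry the PKS label.
- **Intact IgG on SDS-PAGE.** SAP 4.6.2, under secondary efficacy analyses, takes the proportion of patients "who reached the success criterium, will be summarized in a table using the PKS set". This is Table 14.2.18.

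SAP 4.1 assigns FAS and PPS to efficacy, the safety set (SAF) to safety and the PKS to PK data, as a general rule. SAP 4.7 adds: "Safety parameters will be evaluated for the safety analysis data set".

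SAP section 5 explains why the PKS was limited to imlifidase patients: PK and ADA do not apply to the others. It also drops the between-arm comparison of intact IgG, because comparator patients can only score 5. It does not say why ADA or intact IgG should follow the PK analyst's further exclusions.

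**The concern.** Leaving out a patient whose concentration-time profile cannot be interpreted is reasonable when estimating half-life or clearance. It is not a reason to leave the same patient out of the antibody results, or out of a count of who had their IgG cleaved. Both of those questions are about everyone who was dosed.

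As written, one person's judgement about suitability for PK also sets the denominator of a secondary efficacy proportion and of all ADA reporting. Membership is settled with treatment known (SAP 2.3 describes a fully unblinded study) and without a written criterion. At stake is whether these two results describe all dosed patients or a subset chosen for another purpose.

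**Working it through.** The plan gives no figure for this point. Its one design figure, a 95% CI about 8 points wide for the primary comparison, reproduces as 2 × 2.048 × 5 × √(1/20 + 1/10) = 7.93 (SD 5, the midpoint of the stated 4 and 6), but it has no bearing here. The check is mainly a comparison of the set definitions with the output list.

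**Step 1: which outputs depend on the PKS, and is there a copy on another set?**

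| Result | Output | Set | Output on another set |
|---|---|---|---|
| ADA summary | Table 14.4.6 | PKS | none |
| ADA box plot | Figure 15.1.41 | PKS | none |
| ADA IgG and IgE listings | 16.4.1.13, 16.4.1.14 | PKS | none |
| Intact-IgG success proportion | Table 14.2.18 | PKS | scores in Table 14.2.17 and Listing 16.2.1.11 (both FAS) |
| IgG below 5% of baseline | SAP 4.6.2 and Table 14.2.16 | FAS | not affected |

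A patient removed from the PKS therefore disappears from every ADA output. The same patient's SDS-PAGE scores stay in the FAS table and listing. Because success is a score of 0 to 3 at one or more time points before IVIg, the proportion can be recounted from Listing 16.2.1.11 and the time IVIg started.

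**Step 2: does the stated reason require analyst exclusions?** Section 5 needs PE patients left out. The SAF patients who received any imlifidase, and the FAS patients who received any imlifidase, both achieve that. The analyst's further step adds nothing to that purpose.

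**Step 3: size for Table 14.2.18.** Planned imlifidase patients: 20 (SAP 2.2), so each removal is 1/20 = 5% of the denominator. The numbers of failures and exclusions are not in the documents, so the rows below are assumptions that show the range. Let k be the failures among 20, and suppose k patients are removed.

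| k | All dosed | All k failures removed | k successes removed |
|---|---|---|---|
| 0 | 20/20 = 100% | no change | no change |
| 1 | 19/20 = 95.0% | 19/19 = 100% | 18/19 = 94.7% |
| 2 | 18/20 = 90.0% | 18/18 = 100% | 16/18 = 88.9% |
| 3 | 17/20 = 85.0% | 17/17 = 100% | 14/17 = 82.4% |

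The reported proportion can move either way. It moves most if the removed patients are the failures.

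**Step 4: size for ADA.** The SAP treats ADA as numerical and gives no expected level or spread, so no effect on the summary can be calculated. What can be said is that up to 1 in 20 of the planned data is lost per exclusion, with nothing elsewhere to restore it.

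**The case against.** A reader might infer that patients with an interrupted infusion, a partial dose or added PE will drop out, and that cleavage will then look more complete and immunogenicity milder. The documents do not support that. Stopping the infusion for a reaction is what protocol 4.5 instructs. Protocol 1.3, 3.1 and 5.3 allow PE or other standard treatment in the imlifidase arm. A partial dose is covered by the entry rule of SAP 3.4. None of these is in itself a deviation or non-compliance. The open wording would permit exclusion but does not call for it, and nothing fixes the direction of any bias.

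A reader might also infer a flat contradiction with SAP 4.7. It is softer than that. The set rule in SAP 4.1 is stated as general, and the choices in 4.6.2 and 4.7.2 are explicit. The endpoint list in SAP 1.1.2 names ADA separately from the safety parameters, the objectives group immunogenicity with PK and PD, and protocol 7.1.6 places it outside the safety assessments. On the other side, SAP 4.7.2 and Table 14.4.6 sit under safety headings.

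There are real controls. Sets are decided before database lock and recorded in the minutes, PKS counts appear in the disposition table, and deviations are listed by patient. Both results are secondary, descriptive and centrally assayed. The intact-IgG criterion needs only one time point, so failures may be few.

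All of this limits the likely harm. It does not supply a reason for the analyst's exclusions to govern these results, and it does not give ADA a fallback.

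**Conclusion.** The point holds as a matter of set definition. Two results that should describe every imlifidase-treated patient are tied to a set whose final membership is discretionary, and the SAP's own reason for using that set does not need the discretion.

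The exposure is unequal. For ADA, any exclusion is a complete loss from the planned outputs. For Table 14.2.18 each exclusion changes a planned denominator of 20 by one, and the loss is recoverable from FAS outputs. The endpoint of IgG below 5% of baseline and the primary endpoint are untouched.

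This rests on the planned 20 imlifidase patients and on reading SAP 3.4 as allowing removals. It does not rest on any prediction that removals will happen, or that they would favour imlifidase. The percentages in the table are illustrations, not estimates. This is an improvement worth making because it is nearly free, not a threat to the trial's main conclusion.

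**What to change.** Keep the PKS, as the PK analyst defines it, for imlifidase concentrations and PK parameters only: Tables 14.2.21 and 14.2.22 with their figures and listings.

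Run Table 14.4.6, Figure 15.1.41 and Listings 16.4.1.13 and 16.4.1.14 on all SAF patients who received any imlifidase. Run Table 14.2.18 on all FAS patients who received any imlifidase, so that it rests on the same imlifidase patients as Table 14.2.17. State in both places that nobody is removed for deviations or non-compliance. PE patients stay out, as SAP section 5 intends.

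The cost is a population label on five outputs and the matching sentences in SAP 4.6.2, 4.7.2 and section 5. If no dosed patient is excluded from the PKS, the results are identical.

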4.1 General considerations

In general FAS and PPS are used to efficacy data, SAF are used on safety data and PKS is used on Pharmacokinetics (PK) data.

4.1.1 Data presentation

No formal statistical hypothesis testing will be performed in this study.

The data will be presented descriptive and for some of the endpoints 95% confidence intervals for the treatment difference will be presented.

Numerical data will be presented in summary tables by number of patients, arithmetic mean, median, standard deviation (SD), minimum and maximum.

When numerical data are recorded at different time points, absolute values at each time point and changes from baseline may be presented in the summary tables.

Categorical data will be presented by frequency and percent of patients. Number of events will also be reported where applicable.

Summary tables will in general be presented by treatment group and total across treatment groups unless this is not appropriate for specific tables.

Data will be listed by treatment group, patient and time point (if applicable).

4.1.2 Baseline definition

Baseline value is defined as the last non-missing assessment before the patients start on the treatment. Change from baseline will be calculated as the difference between values for a given timepoint after baseline and baseline values (timepoint after baseline value minus baseline value). If the post-baseline value or baseline value are missing, then the change from baseline will also be missing.

4.1.3 Multiplicity

The study is descriptive so no multiple testing will be done. This study will not include any interim analyses.

4.1.4 Data imputation

In general, missing data will remain as missing and the missing values will not be adjusted. There are some exceptions described below.

Adverse events

Missing values will be treated as missing except for causality, toxicity, intensity, seriousness and outcome of an AE, in which case a “worst case” approach will be taken. If causality is missing, it will be set to “related”. If intensity is missing, it will be set to “severe”. If seriousness is missing, it will be considered as a Serious Adverse Event (SAE). If outcome is missing and no date is given for the outcome it will set to “not yet recovered”.

Dates for adverse event and concomitant medication

Missing or partial start dates for AEs and concomitant medication data will be handled in the following way:

- If the start date is totally missing, the date will still be missing.
- If the start date is partial where only months and year are given, then the two cases are considered:
 - 1 If the available partial date (month and year) is before the month and year of treatment start date, then the AE/medication will be considered as pre-treatment and the date will be imputed as the start (1st) of the month.
 - 2 If the available partial date does not indicate that the AE/medication has started before the treatment start, then the AE/medication will be considered as treatment emergent/concomitant. The date will be imputed as the start (1st) of the month (if the month is not same as that of the treatment start date) or treatment start date (if the month is same as the treatment start date).
- If the start date is partial where only the year is given, then the two cases are considered:
 - 3 If the available partial date (year) is clearly before the year of treatment start date, then the start date is imputed as start of the year (1st January YYYY).
 - 4 If the available partial date (year) is equal to or after the year of treatment start date, then the start date will be imputed as start of the year (1st January YYYY) (if the year is not same as that of the treatment start date) or treatment start date (if the year is same as the treatment start date).
- For the partial end dates, similar procedure will be used as for the start dates. The only difference is the imputation for missing days and months. Missing days is imputed to the end of the month instead of the start of the month. If only year is available, the end date is set to 31st December YYYY. It will be checked that the imputed end dates fall after the corresponding start dates.

All completely missing end dates will be missing.

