5.7. Concomitant Medication(s) and Therapy

Maintenance immunosuppression such as tacrolimus, mycophenolate mofetil, cyclosporine A, prednisolone and others are prescribed at the discretion of the treating physician or investigator according to SOC. These drugs can be used the same day as the infusion of imlifidase and be continued during the treatment of AMR. No specific maintenance immunosuppressive treatment in addition to what the patient already has is needed within the study.

Other concomitant medication and/or other therapy considered necessary for the patient's welfare may be given at the discretion of the investigator. All concomitant medication and other therapy, including i.e., premedication, prophylactic antibiotics, steroids and PE, must be recorded on the concomitant medication page in the CRF throughout the study, beginning from screening to end of study. Recorded information will include indication, name of drug or therapy, dose (if available), route of administration and start and stop date.

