4.4 Demographics and other baseline characteristics

The following demographic variables will be summarised by treatment: Age, sex, race, height, weight and Body Mass Index (BMI). The table will be made for FAS. The demographics variables will also be listed by patient.

Medical and surgical history and concomitant illness will be summarised by using latest effective version of Medical Dictionary for Regulatory Activities (MedDRA), System Organ Class (SOC) and Preferred Term (PT). The FAS dataset will be used. Medical and surgical history and concomitant illness will also be presented in a list by patient.

Only concomitant medication during the treatment will be tabulated by World Health Organization (WHO) drug version 153E, level 4 (chemical/therapeutic/pharmacological subgroup) and level 5 (Chemical substance). The FAS dataset will be used. Concomitant medication during the treatment and before the start of the treatment will be presented in a list.

Previous kidney transplant history will be presented in a summary table by treatment and listed by patient. The FAS set will be used.

The donor type (living or deceased) will be listed by patient.

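### The SAP's partial-date rule classes medication by start date alone, so a drug still being taken can be labelled pre-treatment and, read literally, left out of the concomitant-medication table

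*SAP*

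**What the plan says.** SAP 4.1.4 handles partial start dates for adverse events and concomitant medication together, in four numbered cases.

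- Case 1 (month and year known): if the partial date "is before the month and year of treatment start date, then the AE/medication will be considered as pre-treatment". The date is set to the first of that month.
- Case 2 (month and year known): if the partial date "does not indicate that the AE/medication has started before the treatment start, then the AE/medication will be considered as treatment emergent/concomitant". The date is set to the first of the month, or to the "treatment start date (if the month is same as the treatment start date").
- Case 3 (year only): if the year "is clearly before the year of treatment start date, then the start date is imputed as start of the year". No class is given.
- Case 4 (year only, same year as treatment or later): a date is imputed, which is the treatment start date when the years match. No class is given.

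On stop dates the section says "For the partial end dates, similar procedure will be used as for the start dates", with missing days and months filled to the end of the period, and "All completely missing end dates will be missing". It adds a check that imputed end dates come after their start dates.

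SAP 4.4 governs the output: "Only concomitant medication during the treatment will be tabulated". That is Table 14.1.5. Medication during and before treatment is also listed by patient (Listings 16.1.1.6 and 16.1.1.7).

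Protocol 5.7 says of maintenance immunosuppressants: "These drugs can be used the same day as the infusion of imlifidase and be continued during the treatment of AMR". It also has start and stop dates recorded for all concomitant medication.

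**The concern.** An adverse event is treatment-emergent because of when it began, so a start-date rule suits it. A medication is concomitant because it was being taken during treatment, and that depends on when it stopped. Case 1 applies the first logic to the second question. Kidney recipients normally come into this trial already on maintenance immunosuppression, which Protocol 5.7 lets continue through AMR treatment. Those are drugs with starts before the treatment month, so case 1 reaches them whenever the day is missing.

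What is at stake is the by-arm summary of background therapy in an open-label, unstratified comparison of 20 against 10 patients. A table that leaves out drugs in current use, or counts courses that had ended, misdescribes that background.

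**Working it through.** The plan states no figure on this point, so there is none to reproduce. The check applies the four cases literally to invented records and compares the result with an overlap rule: concomitant if the drug is ongoing or its stop date is on or after treatment start. Treatment start is assumed to be 20 June 2021, for illustration only.

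| Record | SAP 4.1.4: class, imputed start | Overlap rule |
|---|---|---|
| A. Start Mar 2019, ongoing | pre-treatment, 1 Mar 2019 (case 1) | concomitant |
| B. Start May 2021, ongoing | pre-treatment, 1 May 2021 (case 1) | concomitant |
| C. Start 2020 (year only), ongoing | no class, 1 Jan 2020 (case 3) | concomitant |
| D. Start May 2021, stop 28 May 2021 | pre-treatment, 1 May 2021 (case 1) | previous |
| E. Start June 2021, stop 12 June 2021 | concomitant, 20 June 2021 (case 2) | previous |
| F. Start 2021 (year only), stop 12 Feb 2021 | no class, 20 June 2021 (case 4) | previous |
| G. Start July 2021, stop 9 July 2021 | concomitant, 1 July 2021 (case 2) | concomitant |

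1. *Ongoing drugs (A, B).* Both are in use on the treatment day and both are labelled pre-treatment. With SAP 4.4 tabulating only concomitant medication, the label puts them outside Table 14.1.5.
2. *Stopped courses (E).* The imputed start is 20 − 12 = 8 days after the recorded stop, and the course is counted as concomitant. The order check does not catch this. It covers imputed end dates, and here the end date is complete while the start was imputed.
3. *Year-only starts (C, F).* They get a date and no class. F also has a start after its own stop.
4. *Date precision.* The cases cover only partial dates. An ongoing drug with a full start date is not reached by case 1 and could enter the table under SAP 4.4. The same drug with the day missing is called pre-treatment. The class then depends on how completely the date was recorded.
5. *Agreement.* D and G get the same class under both rules, so the overlap rule changes only the records that the start-date rule gets wrong or leaves open.

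Size per patient, using the planned arm sizes in SAP 2.4: 1/10 = 10 percentage points in the PE arm and 1/20 = 5 percentage points in the imlifidase arm, for any one drug row.

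**The case against.** The strongest reply is that SAP 4.1.4 imputes dates, while SAP 4.4 decides what is tabulated. A drug begun in 2019 and still taken is in use during treatment, so a programmer working from 4.4 could include it and read the pre-treatment label as describing only when it began. Part of this stands: 4.4 does pull that way, so exclusion is the literal result and not a certainty. But case 1 assigns a class as well as a date, and case 2 pairs treatment-emergent with concomitant, which shows that the class is meant to sort medication. The two sections conflict, and the SAP does not say which governs.

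The wording on end dates might be offered as a remedy. It does not help an ongoing drug that has no end date, because a completely missing end date stays missing and is not said to mean ongoing.

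The listings are a fair answer to any claim that data are lost. Every such drug remains listed by patient, and with 30 patients a reader can work through them. They do not give the by-arm counts that the table is for.

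The stopped-course fault is narrow. It needs a course that began and ended before treatment within the treatment month, with the start day unknown.

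Three stronger readings are tempting and not supported:

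- *That a large share of the table would be missing.* The documents give no rate of partial dates and no number of long-term drugs per patient. The table counts patients, so one qualifying record of a drug is enough. Prednisolone, one of the four drugs that Protocol 5.7 names, is also given to all patients during the study under Protocol 5.3.
- *That the loss would differ by site or by time since transplant.* Nothing in the documents shows this.
- *That the reader could not judge background therapy, or that it is the main rival explanation for DSA differences.* The listings answer the first. The documents do not support the second: steroids, IVIg and rituximab are specified for all patients, the exposure table reports IVIg and rituximab timing, and PE and immunoadsorption sessions are summarised separately.

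**Conclusion.** The point holds as a minor one. For month/year starts, SAP 4.1.4 states a rule that gives the wrong class for a drug still being taken, and that conflicts with SAP 4.4. For a course that started and ended before treatment in the treatment month, it gives the wrong class and an impossible date order. For year-only starts it gives no class.

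The effect stays within the descriptive medication table. One misclassified patient moves a drug's percentage by 10 points in the PE arm or 5 in the imlifidase arm, assuming the planned 10 and 20 patients and no other qualifying record of that drug. The number of affected records cannot be estimated from the documents. The primary DSA endpoint and its confidence interval do not use the concomitant flag, so neither changes.

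**What to change.** In SAP 4.1.4, keep the start-date rule for adverse events and give medication a separate rule that applies at every level of date precision:

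- A medication is concomitant if it is ongoing at treatment start, or if its recorded or imputed stop date is on or after treatment start.
- It is previous only if it stopped before treatment start.
- An imputed start date may not fall after a recorded stop date.

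The text should also say whether a wholly missing stop date counts as ongoing, since the rule depends on it. SAP 4.4 can then refer to this definition, which removes the conflict.

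The cost is a few sentences in the SAP and a revised flag in the ADaM program. Stop dates are already collected under Protocol 5.7, so no new data are needed.
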